Neurological examination c			X		X	X
ECG e			X		X	X
Vital signs f	X	X	X		X	X
Adverse events	X	X	X	X	X	X
Concomitant medications	X	X	X	X	X	X
ePRO diary daily patient entries	X	X	X	X	X	X
Headache medication log	X	X	X	X	X	X
Clinical Laboratory Tests and Sampling Schedule						
Hematology			X		X	X
Clinical chemistry			X		X	X
HbA1c			X		X	X
Urinalysis			X		X	X
Serum Pregnancy (for women of childbearing potential) g			X		X	X
Urine pregnancy g	X	X				
Immunogenicity h			X		X	X
PK blood sample h			X		X	X
Study drug administered i	X	X				
Scales, Questionnaires, and Outcome Measures						
MIDAS			X		X	X
MSQv2.1	X	X	X		X	X
MIBS-4	X	X	X		X	X
PGI-S			X		X	X
GAD-7			X		X	X
PHQ-9			X		X	X

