**Study Period IV:** Patients who complete the double-blind period of this study can opt to enter an open-label period (Study Period IV) for up to 3 months of treatment with 120-mg/month galcanezumab. Following completion of the double-blind period Visit 7 (Month 3) assessments and procedures, patients may enroll in the open-label period of the study and receive open-label study drug. Sites and patients will remain blinded to patients' previous treatment assignments. To preserve blinding at Visit 7, each patient in any treatment group will receive 2 injections: patients randomized to placebo will receive an initial loading dose of 240-mg galcanezumab (2 injections of 120-mg galcanezumab at Visit 7 only); patients randomized to galcanezumab will continue the dose of 120 mg but also receive 2 injections (1 placebo injection and 1 120-mg galcanezumab injection at Visit 7 only). All patients will remain at the office for a 30-minute post-injection observation at this visit. At Visit 8 and Visit 9, all patients will receive a dose of 120-mg galcanezumab. Patients will continue to have efficacy and safety assessed, including daily completion of the ePRO diary and headache medication log (see Section 2, Schedule of Activities). Patients may continue to take their allowed acute migraine or headache medication as in Study Period III.

**Study Period V:** Patients who complete open-label treatment phase or discontinue for any reason during Study Period III or IV must enter into Study Period V for assessment during washout of investigational study drug. During this 4-month phase, sites and patients will remain blinded to patients' treatment assignments. Patients will follow all study procedures during Study Period V but will not receive galcanezumab or placebo. After completion of Visit 10 (Month 6) assessments, if clinically warranted due to a worsening of symptoms, patients may start migraine prevention medications at the discretion of the investigator. The list of allowed preventive medications will be provided separately. At Visit 12 (Month 10), patients will return to the site for their last study visit and be discharged from the study.

Visit 11 (Month 8) will be a virtual visit through telephone by site staff and is to include a review of any spontaneously reported AEs, queries on concomitant medications, and ePRO diary entries since last visit.

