#### **10.3.4.3. Vital Signs and Weight**

Vital signs collected during the study include systolic and diastolic blood pressure, pulse, and temperature. Blood pressure and pulse measurements will be taken when the patient is in a sitting position. Three measurements of sitting blood pressure and pulse will be collected at every visit (except for Visit 2 and phone visits); the 3 sitting blood pressure and pulse measurements will be averaged and used as the value for that visit for analysis.

The incidence rates of patients with treatment-emergent vital sign and weight changes based at any time postbaseline will be assessed using the Fisher's exact test. Specific criteria for treatment-emergent definition will be documented in the SAP.

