Post-treatment-emergent changes in temperature and weight	Post-treatment population with a baseline and at least 1 postbaseline observation	Low: Min of Visits 1–10 High: Max of Visits 1–10	Low: Min of Visits 10.01–12 High: Max of Visits 10.01–12
Post-treatment-emergent changes in blood pressures, pulse, and ECGs	Post-treatment population with a baseline and at least 1 postbaseline observation	Low: Last of Visits 1–10 High: Last of Visits 1–10	Low: Min of Visits 10.01–12 High: Max of Visits 10.01–12
Continuous safety analyses – change from baseline to LOCF endpoint (ANCOVA)	Post-treatment population with a baseline and at least 1 postbaseline observation	Last of Visits 1–10	Last of Visits 10.01–12
Study Periods III / IV / V Combined			
Efficacy/Health outcome analyses	ITT population with a baseline and at least 1 postbaseline observation	Visit 3	All scheduled visits $3 < \text{Visits} \leq 12$
Continuous safety analyses (repeated measures)	Safety population with a baseline and at least 1 postbaseline observation	Last of Visits 1–3	All scheduled visits $3 < \text{Visits} \leq 12$
Treatment-emergent immunogenicity	Safety population - GMB-treated patients with a baseline and at least 1 postbaseline observation	Visit 3	All Visits 3.01–12

Patient Population with Baseline and Postbaseline Definitions by Study Period and Type of Analysis

Study Period/Analysis	Patient Population	Baseline Observation	Postbaseline Observation(s)
GMB-Treated Time			
Treatment-emergent adverse events	GMB-treated population	All Visits 1–3 before double-blind phase dosing for patients treated with GMB during SP III; All Visits 1–7 before open-label phase dosing for patients treated with placebo during SP III*a	All visits after first dosing of GMB through Visit 10
Serious adverse events, discontinuations due to adverse events	GMB-treated population	NA	All visits after first dosing of GMB through Visit 10
Treatment-emergent abnormal laboratory values	GMB-treated population with normal (with respect to direction being analyzed) laboratory values at all non-missing baseline visits and who have at least 1 postbaseline observation	Visits 1–3 before double-blind phase dosing for patients treated with GMB during SP III; Visits 1–7 before open-label phase dosing for patients treated with placebo during SP III	All visits after first dosing of GMB through Visit 10: Visits 3.01–10 for GMB-treated patients during SP III; Visits 7.01–10 for placebo-treated patients during SP III

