- For continuous analyses of temperature and weight, last non-missing baseline during the baseline period will be used as the baseline.
- For the analyses of categorical changes of interest in temperature and weight,
 - the baseline is defined as the minimum value during baseline period when the direction is low.
 - the baseline is defined as the maximum value during the baseline period when the direction is high.

Table CGAX. 6.3 Criteria for Categorical Changes of Interest in Vital Signs and Weight

Parameter	Direction	Criteria	Patients Population defined by Baseline Categories
Systolic BP (mm Hg) (sitting)	Low	≤ 90 and decrease ≥ 20	All patients; >90 ; ≤ 90
	High	≥ 140 and increase ≥ 20	All patients; <140 ; ≥ 140
	PCS High	≥ 180 and increase ≥ 20	All Patients; <180 ; ≥ 180
	Sustained Elevation	≥ 140 and increase ≥ 20 at 2 consecutive visits	All patients; < 140 ; ≥ 140
Diastolic BP (mm Hg) (sitting)	Low	≤ 50 and decrease ≥ 10	All patients; >50 ; ≤ 50
	High	≥ 90 and increase ≥ 10	All patients; <90 ; ≥ 90
	PCS High	≥ 105 and increase ≥ 15	All Patients; <105 ; ≥ 105
	Sustained Elevation	≥ 90 and increase ≥ 10 at 2 consecutive visits	All patients; < 90 ; ≥ 90
Systolic BP or Diastolic BP (mm Hg) (sitting)	Sustained Elevation	Meeting criteria for systolic BP for 2 consecutive visits or meeting criteria for diastolic BP for 2 consecutive visits or both	All Patients
Pulse (bpm) (sitting)	Low	<50 and decrease ≥ 15	All patients; ≥ 50 ; <50
	High	>100 and increase ≥ 15	All patients; ≤ 100 ; >100
	Sustained Elevation	>100 and increase ≥ 15 at 2 consecutive visits	All patients; ≤ 100 ; >100
Weight (kg)	Low	(Loss) decrease $\geq 7\%$	All patients
	High	(Gain) increase $\geq 7\%$	All patients
Temperature ($^{\circ}$ F)	Low	$<96^{\circ}$ F and decrease $\geq 2^{\circ}$ F	$\geq 96^{\circ}$ F
	High	$\geq 101^{\circ}$ F and increase $\geq 2^{\circ}$ F	$<101^{\circ}$ F

Abbreviations: BP = blood pressure; bpm = beats per minute; F = degrees Fahrenheit; kg = kilograms; mm Hg = millimeters of mercury; PCS= Potentially Clinically Significant.

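### Sustained blood-pressure or pulse elevation cannot be met from scheduled visits in Study Period V, yet patients with a single reading would be counted as non-events

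*SAP*

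**What the plan says.** SAP 6.14.4, Table CGAX. 6.3, gives sustained-elevation criteria for systolic pressure ("≥ 140 and increase ≥ 20 at 2 consecutive visits"), diastolic pressure ("≥ 90 and increase ≥ 10 at 2 consecutive visits") and pulse (">100 and increase ≥ 15 at 2 consecutive visits"). A combined blood-pressure row reads "Meeting criteria for systolic BP for 2 consecutive visits or meeting criteria for diastolic BP for 2 consecutive visits or both". The table ties no criterion to a study period.

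SAP 6.1, Table CGAX. 6.1, lists for SP V an analysis of "Post-treatment-emergent changes in blood pressures, pulse, and ECGs". Baseline is the last value in Visits 1–10 and the postbaseline window is Visits 10.01–12. The population is every post-treatment patient with a baseline and one or more postbaseline values. No exception is made for the sustained criteria.

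The Schedule of Activities (Protocol Section 2) marks vital signs at Visits 5, 6 and 7, at Visits 8, 9 and 10, and at Visit 12, with the Visit 11 cell blank. Protocol 5.1 states that "Visit 11 (Month 8) will be a virtual visit through telephone by site staff", and Protocol 10.3.4.3 excludes telephone visits from blood-pressure and pulse collection.

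**The concern.** A rule that needs two consecutive visits is applied to a phase that schedules one. A patient seen only at Visit 12 enters the SP V denominator and can only be counted as not sustained, although the criterion could not be evaluated. Nothing in the SAP separates that patient from one who was assessed and found normal.

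Protocol 5.4 gives the post-treatment phase the purpose of evaluating safety during washout. A sustained-elevation row near zero in that phase would carry almost no information, and the table would not say so. The High and Low categories have a milder form of the same problem. They use the highest or lowest postbaseline value, which comes from three scheduled readings in SP III and SP IV and from one in SP V.

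**Working it through.** **Inputs.** The two-visit rule is from SAP Table CGAX. 6.3. The reading schedule is from Protocol Section 2. The baseline and postbaseline windows are from SAP Table CGAX. 6.1. A reading here means one visit value (the average of three measurements, Protocol 10.3.4.3). The documents give no expected rate of sustained elevation, so there is no plan figure to reproduce. They give no blood-pressure or pulse means or SDs either, so the rates in steps 3 to 5 rest on stated assumptions.

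**Step 1: count.** Consecutive pairs = scheduled readings − 1.

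| Period | Baseline window | Scheduled postbaseline readings | Pairs |
|---|---|---|---|
| SP III | Visits 1–3 | Visits 5, 6, 7 (3) | 2 |
| SP IV | Visits 1–7 | Visits 8, 9, 10 (3) | 2 |
| SP V | Visits 1–10 | Visit 12 (1) | 0 |

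Visit 10 cannot complete a pair because it belongs to the SP V baseline window. A patient who leaves during SP V has one early-termination visit in place of Visit 12, so the count stays at one.

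**Step 2: denominator.** Entry needs one postbaseline value and the criterion needs two. Patients with exactly one are therefore in the denominator and cannot be in the numerator.

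**Step 3: size for the sustained rows.** Let p be the chance of meeting the criterion at a visit and ρ the correlation between neighbouring visits, the same in every period. Put p11 = p + ρ(1 − p) and p01 = p(1 − ρ).

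- One reading: 0.
- Two readings: p × p11.
- Three readings: p × p11 + (1 − p) × p01 × p11.

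Assume p from 2% to 10% and ρ from 0 to 0.6.

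- Low end (p = 0.02, ρ = 0): p11 = p01 = 0.02. Two readings: 0.0004 = 0.04%. Three readings: 0.0004 + 0.98 × 0.02 × 0.02 = 0.00079, or 0.08%.
- High end (p = 0.10, ρ = 0.6): p11 = 0.64, p01 = 0.04. Two readings: 0.064 = 6.4%. Three readings: 0.064 + 0.9 × 0.04 × 0.64 = 0.0870, or 8.7%.

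If a share u of patients has one extra unscheduled SP V reading that counts, the SP V rate is u × p × p11. That is 0.01 × 0.04% = 0.0004% at the low end with u = 1%, and 0.10 × 6.4% = 0.64% at the high end with u = 10%. Dividing by the three-reading rate gives u / [1 + (1 − p)(1 − ρ)]. With u = 10% this is 0.10/1.98 = 5% to 0.10/1.36 = 7%, so SP V would show about 5% to 7% of the rate seen in SP III or SP IV with nothing changed in the patients. If vital signs were taken on everyone at Visit 11, the SP V range would be 0.04% to 6.4%.

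**Step 4: High category.** A simulation of 400,000 patients with stable pressure, no drug effect and one baseline reading applied the Table CGAX. 6.3 criteria. The means and SDs are assumed.

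| Measure (assumed mean; between-patient SD; visit SD) | High, 3 readings | High, 1 reading | Sustained, 3 readings |
|---|---|---|---|
| Systolic (120; 12; 7 to 11) | 1.6–8.6% | 0.6–3.4% | 0.1–0.9% |
| Diastolic (78; 8; 5 to 8) | 5.5–16.1% | 2.1–6.6% | 0.6–2.3% |

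One reading gives about 40% of the three-reading High rate (for example 0.6/1.6 = 0.38 and 6.6/16.1 = 0.41). Pulse was not simulated.

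**Step 5: would equal readings alone make the phases comparable?** No, because each phase has its own baseline. With an assumed systolic rise of 5 mm Hg that never reverses (mean 120, SD 12, visit SD 9), single-visit High is 4.5% at Visit 7 against Visit 3, but 2.5% at Visit 10 against Visit 7 and 2.5% at Visit 12 against Visit 10. For a diastolic rise of 4 mm Hg (mean 78, SD 8, visit SD 6.5) the figures are 10.5%, 6.4% and 6.6%. Measured against Visit 3, the Visit 12 rates return to 4.5% and 10.4%.

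**The case against.** The case for leaving the plan alone has five parts.

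- **The rate is not exactly zero.** A reader might infer that the SP V sustained rate is 0% by construction. The documents do not support that: the window opens at Visit 10.01, Protocol 10.3.4.1 includes unscheduled visits in categorical safety analyses, and footnote b of the Schedule of Activities allows Visit 11 to be held at the site. This stands. But no vital signs are scheduled at Visit 11 in either form, and the SAP does not say whether an unscheduled visit counts as one of two consecutive visits.
- **No SP V sustained row is explicitly promised.** The Table CGAX. 6.1 entry defines only minimum and maximum values. This stands as a point about silence. Even so, applying the two tables together produces the row by default.
- **No on-drug versus off-drug comparison is planned.** A reader might infer that a fall to near zero after dosing stops shows recovery from a drug effect. The documents plan no such contrast. SP IV and SP V are descriptive (Protocol 10.3.4.1), and the SP V rows count new rises from an SP V baseline. This stands, and the recovery reading should not be attributed to the plan.
- **Safety inference is protected elsewhere.** The randomized SP III comparison uses the same visits in both arms. Galcanezumab-treated time ends at Visit 10. The combined SP III/IV/V repeated-measures analysis uses one pre-treatment baseline through Visit 12. High and potentially clinically significant High remain assessable at Visit 12. All of this stands and limits the consequence.
- **The counts are small.** With 243 patients per arm, the simulated three-reading sustained rates mean about 0 to 2 patients for systolic pressure (0.1% to 0.9%) and 1 to 6 for diastolic (0.6% to 2.3%). This stands under the assumed distributions.

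**Conclusion.** The point holds as a reporting defect confined to SP V. From scheduled visits the sustained criteria cannot be met there, and the stated population counts patients who cannot be assessed as non-events. The rate would be near zero whatever the true rate. That conclusion needs only the schedule and the two SAP tables.

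The sizes do depend on assumptions. The figure of 5% to 7% of the SP III or SP IV rate takes an extra reading in 10% of patients and equal p and ρ across periods. The 40% ratio for High is an illustration under assumed blood-pressure distributions and does not cover pulse. No primary, key secondary or randomized safety comparison is touched.

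**What to change.** In SAP Tables CGAX. 6.1 and 6.3:

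1. Omit the sustained-elevation rows for SP V and mark them not assessable. Alternatively, limit their denominator to patients with at least two postbaseline readings in that period and report how many there are.
2. State whether an unscheduled visit counts as one of two consecutive visits.
3. Footnote that SP V High and Low categories for blood pressure and pulse rest on one scheduled reading, against three in SP III and SP IV, so rates are not comparable across phases.
4. If single-visit proportions at Visits 7, 10 and 12 are shown together, use one common pre-treatment baseline (last of Visits 1–3 for patients randomized to galcanezumab) and show them by randomized group. State the fixed baseline used for the placebo group, whose first galcanezumab dose follows the Visit 7 reading.

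The cost is SAP wording, a footnote and, if item 4 is taken up, one small table from data already collected. No assessment is added. SAP 6.1 allows SAP changes only before unblinding; after that, the handling can be described in the clinical study report.

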6.14.5. Electrocardiograms

Analyses of corrected QT (QTc) interval will be calculated using Fridericia's correction formula, as $QT/RR^{1/3}$ (QTcF (msec)). For the QTcF calculation, the unit for QT is millisecond and the unit for RR is second. For patients with QRS ≥ 120 msec at any time during the study, the QT and QTc interval will be excluded from the analyses. A listing of ECG data for patients with QRS ≥ 120 msec at any time during the study will be provided.

The baseline for ECG is defined as the last non-missing baseline value during the baseline period (See [Table CGAX. 6.1](#)). To be exact,

- For analyses including double-blind treatment phase, the baseline for ECG is defined as the last non-missing value before randomization.

The rationale for using the last available value in the baseline period is to minimize

- the potential confound of discontinuing or dose stabilization of medications that modulate ECG during the screening phase (which is early in the baseline period).
- Similarly, for GMB-treated time, the baseline is defined as the last non-missing value before the patient's first dose of GMB. This baseline definition was chosen to be consistent with the analysis approach for the double-blind treatment phase as described above.

This baseline definition for ECG applies to all analyses (both continuous and categorical, quantitative and qualitative) for ECG.

The baseline and postbaseline values are summarized in [Table CGAX. 6.1](#).

The number and percent of patients meeting criteria for treatment-emergent abnormalities in ECG intervals (PR, QRS, and QTcF) and heart rate at any time during study will be summarized. Treatment group comparisons will be performed using Fisher's exact test.

[Table CGAX. 6.4](#) displays the criteria for treatment-emergent changes in ECG intervals and heart rate. The absolute threshold in the criteria is based on 1) minimum postbaseline when the direction is low; 2) maximum postbaseline when the direction is high.

- For treatment-emergent low analyses: Patients with all normal or high values at baseline (no low values) will be included.
- For treatment-emergent high analyses: Patients with all normal or low values at baseline (no high values) will be included.
- For treatment-emergent increase analyses: Patients with a baseline and at least 1 postbaseline result will be included.

Table CGAX. 6.4 Criteria for Treatment-Emergent Changes in ECG Intervals and Heart Rate

Parameter	Direction	Criteria	
Heart Rate (bpm)	Low	<50 and decrease ≥ 15	
	High	>100 and increase ≥ 15	
PR Interval (msec)	Low	<120	
	High	≥ 220	
QRS Interval (msec)	Low	<60	
	High	≥ 120	
QTcF (msec)	Low	Males: <330	Females: <340
	High	Males: >450	Females: >470
	PCS High	>500 msec	
	Increase	Increase >30 msec	
		Increase >60 msec	
		Increase >75 msec	

Abbreviations: bpm = beats per minute; ECG = electrocardiogram; msec = milliseconds; PCS = potentially clinically significant; QTcF = Fridericia's corrected QT interval.

6.15. Subgroup Analyses

Subgroup analyses will be performed for the primary efficacy measure (change from baseline in the number of MHDs) separately for each of the subgroup populations listed in [Table CGAX. 6.5](#). Subgroup analyses will be conducted only for the ITT patients in Study Period III.

Each of the subgroup analyses for the primary measure of change from baseline in the number of MHDs will be conducted using MMRM. The same MMRM model described in Section 6.10.1 will be used, with terms of subgroup, subgroup-by-treatment, subgroup-by-month, and subgroup-by-treatment-by-month interactions added as additional covariates.

Table CGAX. 6.5 Definition of Subgroup Variables

Subgroup Variable	Categories
Sex	Male, female
Country	China, India, Russia
Baseline number of migraine headache days (MHDs)	2 levels of baseline migraine frequency : 
 • <8 MHDs • ≥8 MHDs

6.16. Protocol Deviations

Protocol deviations will be identified throughout the study. Important protocol deviations (IPDs) are defined as those deviations from the protocol that would potentially compromise patients' safety, data integrity, or study outcome. The details of the categories and subcategories of IPDs and how the IPDs would be identified are contained in a separate document (Trial Issues Management Plan for study CGAX).

A table and listing of important protocol deviations for Intent-to-Treat patients during baseline, double-blind treatment phase, open-label treatment phase, or post-treatment phase, will be provided by each treatment groups and overall.

6.17. Interim Analyses

No interim analyses are planned for this study. If an unplanned interim analysis is deemed necessary, the appropriate Lilly medical director, or designee, will be consulted to determine whether it is necessary to amend the protocol.

This study will include two database locks. The first is to occur after all patients have had the opportunity to complete the 3-month double-blind treatment phase (Study Period III). The purpose of this analysis is the final analysis of the primary efficacy endpoint, as well as efficacy and safety analyses of the double-blind phase. Study sites, patients, and all Lilly personnel directly involved in the continuing trial will remain blinded to patients' double-blind treatment assignment. Unblinding details are specified in a separate unblinding plan document. This

analysis will not be considered an interim analysis because the double-blind phase is of primary interest.

The second database lock will occur at the post-treatment follow-up phase once all patients have had the opportunity to complete the entire study. This reporting database will include all data for all patients enrolled into the study, including all open-label and post-treatment phase data.

6.18. Clinical Trial Registry Analyses

Additional analyses will be performed for the purpose of fulfilling the Clinical Trial Registry (CTR) requirements.

Analyses provided for the CTR requirements include the following:

Summary of adverse events, provided as a dataset which will be converted to an XML file. Both Serious Adverse Events and 'Other' Adverse Events are summarized: by treatment group, by MedDRA preferred term.

- An adverse event is considered 'Serious' whether or not it is a treatment emergent adverse event (TEAE).
- An adverse event is considered in the 'Other' category if it is both a TEAE and is not serious. For each Serious AE and 'Other' AE, for each term and treatment group, the following are provided:
 - the number of patients at risk of an event
 - the number of patients who experienced each event term
 - the number of events experienced.
- Consistent with www.ClinicalTrials.gov requirements, 'Other' AEs that occur in fewer than 5% of patients/subjects in every treatment group may not be included if a 5% threshold is chosen (5% is the minimum threshold).
- AE reporting is consistent with other document disclosures for example, the CSR, manuscripts, and so forth.

7. Unblinding Plan

After the reporting database is locked for statistical analysis of the double-blind treatment phase, a limited number of Lilly personnel will be unblinded to complete the study report and prepare for submission. However, study sites, patients and all Lilly personnel directly involved in the ongoing open-label and post-treatment follow-up phases will remain blinded to patients' double-blind treatment assignment until final database lock. Unblinding details are specified in a separate unblinding plan document.

A final database lock is planned at the end of the study when all patients complete the study. The final analysis will include all data that are collected during the study, including all open-label and post-treatment phase data.

8. References

